The Role of Alpha Melanocyte Stimulating Hormone (α -MSH) in Ocular Disease

NCT03451578

[name]

8/13/18 Revision

Research Summary

Purpose of the Study:

We aim to study the ocular levels of alpha melanocyte stimulating hormone in the aqueous humor of patients with severe geographic atrophy. As there currently are no therapeutic options for these patients, further research into potential therapeutic targets such as α -MSH, is of utmost importance.

Background & Significance:

Macular degeneration is a disease of the retina affecting the elderly. There are two forms of macular degeneration: dry and wet macular degeneration. Wet macular degeneration may be treated with anti-vascular endothelial growth factor (anti-VEGF) injections. Dry macular degeneration is slowly progressive and in its most advanced form causes severe atrophy and vision loss. There is currently no treatment for dry macular degeneration.

The melanocortin system encompasses multiple peptides including α -, β -, γ -melanocyte stimulating hormone (MSH) and adrenocorticotrophic hormone (ACTH). There are five MC receptors (MCR1-5) that are expressed in a multitude of cells and tissues. Alpha melanocyte stimulating hormone is widely expressed in the tissues such as the hypothalamus, skin and retina.¹

There are several known effects of α -MSH including suppressing pro-inflammatory signals, promoting production of anti-inflammatory cytokines, inducing suppressor antigen presenting cells, inducing activation of regulatory T cells, and regulating the immunity in healthy eyes.²⁻⁵

Retina pigment epithelial (RPE) cells have been shown to be a source of α -MSH. RPE cells in culture produce 2 ng of α -MSH in 24 hours. There is possible loss of α -MSH in eyes with autoimmune disease or damaged retinas. Alpha MSH may increase RPE and photoreceptor cell survival. Both RPE and photoreceptors express melanocortin receptors through which alpha MSH promotes cell survival.⁶ In an experimental rat model for example when α -MSH analog was injected into the eyes of rats with retinal dystrophy photoreceptor rescue was seen through to the hormone's neurotrophic activity.⁷ Additionally another study showed α -MSH protected RPE cells against oxidative stress.⁸

Alpha-MSH is a molecule that is extremely prone to proteolysis, even when removed from animal or human eyes it is prone to being quickly denatured. This is why human eyes of living subjects are the best sample for the most accurate analysis of α -MSH

The Role of Alpha Melanocyte Stimulating Hormone (α -MSH) in Ocular Disease

[name]

8/13/18 Revision

levels. Levels in normal eyes undergoing cataract surgery have been previously measured in one study of 8 eyes. The mean level in these eyes was 20pM with a range of 8-31 pM.⁹ As the concentration of α -MSH in the aqueous of normal eyes has previously been published, the next step is to describe levels in eyes with pathology, such as advanced macular degeneration.

Alpha MSH is a hormone that has been shown to be found in the eye. The goal of this study is to see if levels of this hormone are affected by advanced dry macular degeneration. As macular degeneration is a clinical diagnosis based on exam and imaging findings, levels of alpha MSH should not and will not be considered a diagnostic test for this disease.

Currently there are no treatment options for patients with severe geographic atrophy. This is a blinding disease without a therapeutic option. Learning more about the levels of alpha MSH in patients with geographic atrophy may be beneficial in further understanding the disease and potential treatment options.

We hypothesize that eyes with advanced geographic atrophy will have decreased levels of alpha MSH as compared to normal controls. As there are potential ways to supplement α -MSH in the eye and bloodstream, the finding of a low level of alpha MSH would be significant as it may provide a new potential therapeutic pathway to explore. The control used will include the prior published study of levels in 8 human eyes and the normative controls that will be gathered during routine cataract surgery during this study.

Design & Procedures:

If the subject decides to participate, the informed consent process will be completed. After completing the consent form, subjects will be asked to complete a short memory test, the Montreal Cognitive Assessment (MoCA), blind version (attached to IRB submission), to be administered by one of the key personnel. An aqueous paracentesis will be then be performed as follows:

The anterior chamber paracentesis will be performed using povidone iodine preparation and post-procedural topical antibiotics. After informed consent is obtained the eye will be anesthetized using topical anesthesia. The lids will be cleaned with 10% povidone iodine and one drop of 5% povidone iodine will be applied to the ocular surface. A lid speculum will be placed to retract the eyelids. A 27-gauge needle will be placed through the clear cornea to aspirate approximately 100 μ l of aqueous humor. Following the procedure, prophylactic topical antibiotics will be given for 3 days.

The patient will be re-examined for possible immediate complication such as bleeding, hypotony or corneal scratch 20 minutes after the procedure at the slit lamp.

The Role of Alpha Melanocyte Stimulating Hormone (α -MSH) in Ocular Disease

[name]

8/13/18 Revision

In 10 eyes of patients recruited prior to routine cataract surgery a careful anterior chamber paracentesis will be performed through the clear cornea immediately after the sideport incision is made. Care will be taken to avoid inadvertent introduction of blood into the syringe.

Once collected the samples will be frozen at -80 degrees Celsius. The samples will then be sent by secure shipment to an outside lab to measure levels of α -MSH in aqueous samples using ELISA. Specifically, the samples will be sent to [name] at Boston University who is a world expert in the measurement of alpha MSH in the eye using ELISA assays. [name] has IRB approval for the measurement of alpha MSH in ELISA assays at Boston University under approval number H-32859 with original approval date 4/14/14. All of the samples sent to [name] lab will be de-identified so he has no patient health information.

A follow-up phone call will be made 5 days after the procedure for subjects with geographic atrophy to assure the eye feels back to baseline and the patient does not need closer follow-up. Control subjects will be asked to follow with their cataract surgeon for normal post operative checks as per the cataract surgeon (usually day 1, week 1 and month 1 after surgery).

Selection of Subjects:

The subject population will consist of up to 50 volunteers from the Duke Eye Center's vitreoretinal clinic. All subjects will be 60 years of age or older. Subjects with severely limited vision or blindness from geographic atrophy and only those patients who are pseudophakic or aphakic will be included in the study. Subjects must have a best corrected visual acuity of 20/100 or worse in the eye undergoing the procedure. If subjects with advanced macular degeneration are undergoing cataract surgery then the sample of aqueous will be obtained at the time of cataract surgery. Very few patients with geographic atrophy undergo cataract surgery. Enrollment solely from cataract surgery patients would be too low for results from the study to be meaningful. This is due primarily to the fact that in many patients with advanced geographic atrophy in the setting of macular degeneration, cataract surgery has most likely been previously performed due to their age. Second, if cataract surgery has not been performed it is often not recommended as it is unlikely to further improve their vision given the degree of vision loss from geographic atrophy. We propose to include eyes with only severe geographic atrophy with best corrected visual acuity of 20/100 or worse.

Additionally, we will also attempt to get normative data on α -MSH levels to compare to previously reported levels and aim to gather 10 samples in healthy eyes at the time of cataract surgery. Every reasonable attempt will be made to include subjects from all races.

The Role of Alpha Melanocyte Stimulating Hormone (α -MSH) in Ocular Disease

[name]

8/13/18 Revision

Subject Recruitment & Compensation:

Subjects with geographic atrophy and control subjects will be recruited by [name] or [name] from their vitreoretinal clinics during standard-of-care visits at the Duke Eye Center. Controls will also be recruited from [name] patients that are having cataract surgery.

Subjects will not be compensated for their participation in this study.

Consent Process – see Section 14 of the e-IRB submission form and complete the questions in that section.

[name] (Principal Investigator) or other IRB listed staff for this project will conduct the consent process prior to enrolling subjects. Each portion of the consent will be reviewed with the subject with ample time provided to the subject for discussions/questions prior to enrolling onto the study. A copy of the consent will be given to the subject if they choose to participate.

Patients with poor vision will have the consent form read to them in the presence of an impartial witness.

Subject's Capacity to Give Legally Effective Consent:

Only subjects able to understand the informed consent process and with legal capacity to give consent will be included in the study.

Study Interventions:

There will be no study interventions apart from those described in #4 above.

Risk/Benefit Assessment:

While these patients will have significantly limited vision due to exceedingly advanced macular degeneration, the study poses certain risks to the patient. There is a low but serious risk of inoculation of the eye with an infectious organism. The risk of endophthalmitis from aqueous paracentesis has not been published or studied, however is much lower than that of a vitreous tap or intravitreal injection, which has a low rate of endophthalmitis of 0.05% or less. The previously published studies of patients undergoing AC paracentesis for uveitis have reported a 0% rate of serious infection such as endophthalmitis.^{10,11}

Other risks to consider include bleeding due to pressure change or inadvertent damage to the ocular structures by the needle and leaking from the needle track. A corneal

The Role of Alpha Melanocyte Stimulating Hormone (α -MSH) in Ocular Disease

[name]

8/13/18 Revision

scratch may also occur during this procedure. Precautions, such as cleaning of the eye prior to the procedure and antibiotic use after the procedure, will be taken to minimize these risks.

We will additionally examine the anterior chamber 20 minutes post-procedure as most complications such as hyphema (bleeding in the eye), leak from the needle track, or corneal scratch would be apparent during this time frame.

As the eyes that will be chosen for the study will be pseudophakic there will be no risk of cataract or trauma to the lens which is the most worried about complication of an aqueous tap.

While study subjects will not receive immediate direct benefit, the data acquired may provide valuable information that will support the potential understanding and possible development of therapeutics in disease without current therapeutic options.

Potential loss of confidentiality is a risk of any study however we will take every precaution to keep patient health information confidential.

Costs to the Subject:

There will be no financial costs to the subjects for study participation. However, the subject would remain responsible for the costs of their clinical care, which are independent of this study.

Data Analysis & Statistical Considerations:

At this stage, only quantitative analysis of alpha MSH levels will be performed.

Data & Safety Monitoring:

We do not anticipate that the risk for adverse events will be any higher than for other commonly performed aqueous paracentesis in the clinic setting. Specifically, we do not anticipate any adverse event as a result of study participation in the study as every precaution will be taken to decrease the risk of potential infection. Additionally, by including only patients who have had prior cataract surgery (pseudophakic) or no lens (aphakic), there is no risk for trauma to the lens or induction of a cataract. The PI's contact information will be available to each enrolled subject should a late event occur. The investigator will review and sign off on all adverse events and problems as they occur and they will be reported to the IRB per Duke IRB policies.

Privacy, Data Storage & Confidentiality – see Section 12 of the e-IRB submission form and complete the questions in that section.

The Role of Alpha Melanocyte Stimulating Hormone (α -MSH) in Ocular Disease

[name]

8/13/18 Revision

Collected clinical data, including a single master list to relink the study ID to the subject, will be stored on password-protected, hard drive encrypted departmental computers in the Department of Ophthalmology. Data will be stored in the P:drive in a secured folder under the PIs name. Only the study staff will have access to these files.

References:

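### Do the eye criteria in Selection of Subjects shut out the protocol's own cataract-surgery controls?

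*Protocol*

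**What the plan says.** All of these statements are in the Protocol.

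- **Population (Selection of Subjects).** "The subject population will consist of up to 50 volunteers from the Duke Eye" Center's vitreoretinal clinic, and "All subjects will be 60 years of age or older".
- **Lens.** After naming people with severe vision loss from GA, the sentence continues that "only those patients who are pseudophakic or aphakic will be included in the study".
- **Acuity.** "Subjects must have a best corrected visual acuity of 20/100 or worse in the eye undergoing the procedure".
- **Disease.** "We propose to include eyes with only severe geographic atrophy with best corrected visual acuity of 20/100 or worse".
- **GA eyes at cataract surgery.** "If subjects with advanced macular degeneration are undergoing cataract surgery then the sample of aqueous will be obtained at the time of cataract surgery". The protocol expects very few of these.
- **Controls.** In a new paragraph, the investigators "aim to gather 10 samples in healthy eyes at the time of cataract surgery". Design & Procedures gives these 10 eyes their own sampling step and leaves their follow-up to the cataract surgeon.
- **Recruitment (Subject Recruitment & Compensation).** "Subjects with geographic atrophy and control subjects will be recruited by [name] or [name] from their vitreoretinal clinics during standard-of-care visits". Controls may also come from a clinician's cataract-surgery list.
- **Lens risk.** Risk/Benefit Assessment and Data & Safety Monitoring say there is no risk to the lens, because the eyes are pseudophakic or aphakic.

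**The concern.** Three eye criteria (lens status, acuity, GA) are worded for subjects or for the study as a whole. A healthy eye awaiting cataract surgery is neither pseudophakic nor aphakic and has no severe GA. Taken at face value, every concurrent control would enter against a written inclusion rule. So would any GA subject sampled at their own cataract surgery.

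If the criteria are confined to the GA group, a second worry appears. Controls must be at least 60, able to consent and at routine cataract surgery, but their eye condition is described only as healthy or normal, with no definition. They come from two sources, one of them a retina clinic. Background & Significance suggests that α-MSH may be lost in eyes with autoimmune disease or a damaged retina. A control eye with such disease could therefore lower the control mean and shrink the GA difference. These 10 eyes are the only controls whose eligibility the investigators can still set, since the other 8 are already published.

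**Working it through.** The first question is one of wording, so I set each criterion against each group.

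| Criterion | GA subject in clinic | GA subject at cataract surgery | Control at cataract surgery |
|---|---|---|---|
| Pseudophakic or aphakic | can meet | cannot meet | cannot meet |
| Acuity 20/100 or worse | can meet | can meet | may or may not meet |
| Severe GA | can meet | can meet | cannot meet |

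**Scope.** Read without context, the lens and disease rows admit 0 of 10 controls. The context points the other way:

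1. The sentence with the lens rule has GA patients as its subject.
2. The rest of that paragraph explains why GA patients seldom have cataract surgery and why their vision is poor.
3. Controls arrive in the next paragraph as an addition.
4. Design & Procedures treats controls separately for sampling and follow-up.
5. Background & Significance states the hypothesis against normal controls and names the newly gathered eyes among them.

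A reading that removes the control group contradicts points 3 to 5, so the criteria belong to the GA group.

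**Acuity.** No conflict is shown. Nothing in the protocol fixes the acuity of a control eye.

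**GA eyes at cataract surgery.** This conflict is real but small. A specific sentence, two sentences after the lens rule, says how these eyes are sampled. It works as an exception that was not labelled as one.

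**Lens-risk statements.** Risk/Benefit Assessment opens with patients whose vision is limited by advanced macular degeneration. Data & Safety Monitoring compares the risk with paracentesis in clinic. Both fit the clinic-sampled GA group. Neither literally covers eyes sampled in the operating room.

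**Size.** Background & Significance gives a mean of 20 pM and a range of 8 to 31 pM in 8 normal eyes. The shift in the control mean when one eye differs from 20 pM is (value − 20)/n.

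- n = 10: (8 − 20)/10 = −1.2 pM; (31 − 20)/10 = +1.1 pM.
- n = 18, if the 8 published eyes are pooled (an assumption): −12/18 = −0.67 pM; 11/18 = +0.61 pM.

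Both ends of that range are values seen in normal eyes, so these shifts describe ordinary variation among eligible controls and do not measure mis-selection. One control eye at the GA level would dilute the difference by 1/10 = 10%, or 1/18 = 5.6%. That assumes one such eye is accepted, and the protocol gives no rate to support it.

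**The case for a change.** The strongest case for a change is that the GA-only reading does not settle everything. The lens rule still clashes with GA subjects sampled at cataract surgery, in the same paragraph. Two later sections rest a statement of no lens risk on that rule. The opening sentence draws the whole population from the retina clinic, while the recruitment section adds a cataract list. Eligibility also belongs in the protocol, so it cannot be left to a statistical analysis plan, and a sentence saying which group each criterion covers would cost little.

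The inconsistency in the lens wording stands, as does the absence of a definition of healthy. The population source does not mislead, because the recruitment section names both sources. The point about control eligibility loses most of its force. Clinicians choosing healthy eyes, some of them from a retina clinic, would probably leave out known retinal disease. The description also matches the published comparator, which was normal eyes at cataract surgery. A written rule whose content the investigators would still have to supply gives no demonstrable gain over the judgement they would use anyway.

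**Conclusion.** No change to the plan follows. The GA, acuity and lens criteria are meant for the GA group, the 10 controls are not excluded, and there is no contradiction on acuity. What is left is a clerical mismatch: the lens statements in Selection of Subjects, Risk/Benefit Assessment and Data & Safety Monitoring do not say which group or sampling setting they cover. If the protocol is revised for other reasons, those statements can be reconciled then.

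No effect on the GA comparison is shown. Its direction would also be uncertain, since the protocol speaks only of a possible loss of α-MSH in some diseased eyes. The conclusion rests on two assumptions: that staff read the criteria in context, and that they apply healthy in its ordinary clinical sense at both recruitment sources. Evidence that diseased eyes were being accepted as controls would reopen the point.

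### Are 10 concurrent controls under a ceiling of 50 too few, so that the protocol should plan about 30 GA eyes and 20 controls instead?

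*Protocol*

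**What the plan says.** On numbers, Selection of Subjects gives a maximum only: "The subject population will consist of up to 50 volunteers". It states no target for GA eyes and does not say whether controls count within the 50. The same section says controls may also come from cataract surgery patients. For controls it says the investigators "aim to gather 10 samples in healthy eyes at the time of cataract surgery", with the purpose of setting normative levels beside those already published, and Design & Procedures gives the same number: "In 10 eyes of patients recruited prior to routine cataract surgery".

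On aims, Background & Significance contains both a comparison and a description. The comparison is in "The goal of this study is to see if levels of this hormone are affected by advanced dry macular degeneration" and in the hypothesis that eyes with "advanced geographic atrophy will have decreased levels of alpha MSH as compared to normal controls". The description is in "the next step is to describe levels in eyes with pathology", and Purpose of the Study likewise speaks of studying levels in patients with severe GA.

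On the control group, the same section does not rely on the 10 new samples alone: "The control used will include the prior published study of levels in 8 human eyes", alongside the new cataract-surgery samples.

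The protocol gives no effect size, SD, alpha, power or precision target. Data Analysis & Statistical Considerations says only that levels will be analysed quantitatively.

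**The concern.** When two groups have similar variability, the smaller one limits the precision of their difference. If the ceiling is filled, the plan could end with 40 GA eyes and 10 controls, or with 50 and 10 if controls are extra. Further GA eyes then add almost nothing to the comparison: going from 40 to 50 with 10 controls lowers the standard error of the difference by only 2%. Shifting about ten places to controls would sharpen the comparison without raising enrolment, and the extra controls would be sampled during surgery that is already planned. At stake would be a real fall in α-MSH missed, or estimated too loosely, for want of a few more normal eyes.

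**Working it through.** There is no sample-size figure in the protocol to reproduce. The check is therefore what a 30 + 20 split would gain and what it would cost.

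**Inputs.** From the protocol: a ceiling of 50, an aim of 10 concurrent controls, and 8 published eyes with mean 20 pM and values from 8 to 31 pM. Assumed: one eye per subject, ceiling filled, and equal SDs unless stated. The readings 40 + 10 (controls inside the 50) and 50 + 10 (controls on top) are both inferred. The second compares 60 subjects with 50.

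**1. Standard error of the difference.** SE = SD × √(1/n_GA + 1/n_C), with n_C the concurrent controls plus whatever weight the 8 published eyes receive.

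| Published eyes | 40 + 10 | 50 + 10 | 30 + 20 | Gain v 40 + 10 | Gain v 50 + 10 |
|---|---|---|---|---|---|
| Not used | √0.1250 = 0.3536 | √0.1200 = 0.3464 | √0.0833 = 0.2887 | 18.4% | 16.7% |
| Counted as 4 | √0.0964 = 0.3105 | √0.0914 = 0.3024 | √0.0750 = 0.2739 | 11.8% | 9.4% |
| Fully pooled | √0.0806 = 0.2838 | √0.0756 = 0.2749 | √0.0690 = 0.2628 | 7.4% | 4.4% |

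SE columns are in units of the SD. The control share of the variance at 40 + 10 is 0.100/0.125 = 80%, or 0.0556/0.0806 = 69% with full pooling.

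**2. In pM.** The protocol gives no SD. Dividing the published range by the expected range of 8 normal values gives (31 − 8)/2.847 = 8.1 pM, a rough assumption. The 95% CI half-width for the difference then goes from 5.8 pM (40 + 10) or 5.6 pM (50 + 10) to 4.7 pM with concurrent controls only. With full pooling it goes from 4.6 or 4.4 to 4.3 pM.

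**3. Cost to the GA mean.** Its SE is SD/√n. Going from 40 to 30 eyes multiplies it by √(40/30) = 1.155, a rise of 15%. Going from 50 to 30 multiplies it by √(50/30) = 1.291, a rise of 29%. At SD 8.1 the SE is 1.28 pM (40), 1.15 pM (50) and 1.48 pM (30).

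**4. If the ceiling is not reached.** The ceiling is a maximum, not a target.
- Total 40, 24 + 16 against 30 + 10: 1 − √(0.1042/0.1333) = 12%. Pooled: 1 − √(0.0833/0.0889) = 3%.
- Total 30, 18 + 12 against 20 + 10: 1 − √(0.1389/0.1500) = 4%. Pooled, both splits give 1/18 + 1/20 = 0.1056, so nothing is gained.

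**5. If the SDs differ.** Suppose GA variance is twice the control variance, so SE = control SD × √(2/n_GA + 1/n_C).
- Against 40 + 10: unpooled √(0.1167/0.1500) = 0.882, a gain of 11.8%; pooled √(0.1024/0.1056) = 0.985, a gain of 1.5%.
- Against 50 + 10, pooled: √(0.1024/0.0956) = 1.035, a loss of 3.5%.

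The gain disappears when the ratio of GA SD to control SD passes a break-even value. Against 40 + 10 this is √[(1/10 − 1/20)/(1/30 − 1/40)] = 2.45, or √[(1/18 − 1/28)/(1/30 − 1/40)] = 1.54 pooled. Against 50 + 10 it is 1.94, or 1.22 pooled. The protocol has no GA data to say where the ratio lies.

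**The case for a change.** The best argument for the concern is that full pooling is optimistic. The protocol itself describes α-MSH as highly prone to breakdown once removed from the eye, so handling can affect measured levels. The published series dates from 1992 according to the reference list. Only the concurrent controls share this study's collection, freezing and assay, and part of their purpose is to check agreement with the published levels. If the two control sets disagree, the comparison may rest on 10 eyes and the gain is then nearest 17% to 18%. For an assumed fall of 8 pM at SD 8.1, two-sided 5%, power would be 78% at 40 + 10 and 92% at 30 + 20 (93% and 96% pooled). The amendment would be small.

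Much of this stands. The arithmetic is right under its assumptions, the weight due to the 8 eyes is open, and a sponsor who cared only about the comparison and expected to fill the ceiling might well choose more controls. It is also true that the text leaves unclear whether controls count toward the 50. That is a separate matter, which could be clarified without adopting any particular split.

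It does not follow that the plan is wrong. The larger gains require giving the published eyes no weight, although the protocol names them as part of the control. The 8 pM effect and the SD of 8.1 are assumptions, so the power figures show no shortfall against anything planned. How the two control sets are combined is commonly left to a statistical analysis plan, which is not shown here. A 30 + 20 split would also decide for the sponsor that controls fall inside the 50.

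**Conclusion.** The concern does not hold as a fault in the plan. Reallocation buys 4% to 7% on the SE of the difference if the published eyes are fully pooled, and 17% to 18% only if they get no weight. The price is a 15% to 29% larger SE for the GA mean. The protocol wants both quantities and does not rank them, so which should have the precision is the investigators' choice. Ten samples also fit the limited normative check that Selection of Subjects assigns to them.

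The gains rest on a ceiling that may not be filled and on equal SDs that nothing in the document supports or refutes. At a total of 30 the gain is 4% or nil, and with GA variance twice the control variance the proposal can be 3.5% worse. With no stated power, precision goal or allocation ratio for 10 controls to miss, this is a preference about design and calls for no correction.

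### The 10 concurrent controls have no age rule beyond a floor of 60, so age may confound the comparison with geographic atrophy eyes; this risk is cheap to reduce.

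*Protocol*

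**What the plan says.** Background & Significance in the protocol sets a comparative aim: "The goal of this study is to see if levels of this hormone are affected by advanced dry macular degeneration". It adds a directional hypothesis: "We hypothesize that eyes with advanced geographic atrophy will have decreased levels of alpha MSH as compared to normal controls". Two control sources are named there: 8 previously published eyes (mean 20 pM, range 8 to 31 pM) and eyes sampled during this study.

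The concurrent controls are described in two places. Design & Procedures has "In 10 eyes of patients recruited prior to routine cataract surgery", and Selection of Subjects says the investigators "aim to gather 10 samples in healthy eyes at the time of cataract surgery".

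GA subjects are defined in Selection of Subjects. Apart from the few who happen to be having cataract surgery, "only those patients who are pseudophakic or aphakic will be included in the study". The section explains that in many GA patients "cataract surgery has most likely been previously performed due to their age". It also gives a reason unrelated to age: surgery is often not advised because little vision would be gained.

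The one age criterion is "All subjects will be 60 years of age or older". No section matches, restricts or balances the two groups on age.

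**The concern.** The comparison is not randomised, so the groups must be made comparable through the choice of controls. Controls are people having cataract surgery now; most GA subjects had it in the past. The protocol itself links earlier surgery to age, which makes an age difference plausible.

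The floor of 60 does little to prevent this, and its reach is uncertain. I read its wording as covering controls. However, the same paragraph also requires that "Subjects must have a best corrected visual acuity of 20/100 or worse in the eye undergoing the procedure", which cannot apply to healthy control eyes. If the floor is likewise meant only for GA subjects, controls have no age rule at all.

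If alpha-MSH falls with age, a lower level in GA eyes could partly reflect age. If it rises with age, a real reduction could be hidden. A later analysis can adjust for age only where the groups overlap, and with 10 controls there may be few or none as old as the GA subjects. That is settled at recruitment.

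**Working it through.** The protocol states no test, effect size or power, so there is no figure of its own to reproduce. The calculation below shows only how large the problem could be.

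**Inputs from the protocol**
- 10 concurrent controls and a floor of 60.
- Up to 50 subjects. Whether this includes the controls is not stated, so I use 40 or 50 GA eyes.
- Published normal mean 20 pM, range 8 to 31 pM, n = 8.

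**Assumptions (not in the protocol)**
- Ages are normal with SD 7, truncated at 60, with means before truncation of 80 (GA) and 72 (controls).
- The correlation r of alpha-MSH with age lies between -0.3 and +0.3.
- The test is a two-sided 5% t-test.

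**1. Age gap and overlap (no test needed).** After truncation the means are 80.0 and 72.7, a gap of 7.4 years. The share of controls aged 80 or over is 0.132, so P(none of 10) = (1 - 0.132)^10 = 0.24. For control means of 70 and 74 the shares are 0.083 and 0.200, giving 0.42 and 0.11. About half of GA subjects are 80 or over (39% to 61% for GA means of 78 to 82).

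**2. Spurious difference.** The SD implied by the range is (31 - 8)/2.847 = 8.1 pM, where 2.847 is the expected range of 8 standard normal values. Bias in SD units is r × gap/7.
- r = -0.1, gap 5: -0.071 SD × 8.1 = -0.6 pM.
- r = -0.3, gap 7.4: -0.317 SD × 8.1 = -2.6 pM.
- r = 0 or gap 0: no bias.

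**3. False-positive rate.** This comes from the noncentral t distribution with noncentrality = bias/√(1/n_GA + 1/10). For 40 vs 10, √(0.025 + 0.1) = 0.354.

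| r | gap 5 | gap 7.4 | gap 8 | gap 7.4, 50 vs 10 |
|---|---|---|---|---|
| 0 | 5.0% | 5.0% | 5.0% | 5.0% |
| -0.1 | 5.5% | 6.0% | 6.2% | 6.0% |
| -0.2 | 6.8% | 9.0% | 9.7% | 9.2% |
| -0.3 | 9.1% | 14.2% | 15.8% | 14.7% |

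**4. Opposite trend.** For a true reduction of 1 SD (40 vs 10, gap 7.4), power is 79% at r = 0 and 70%, 59% and 47% at r = +0.1, +0.2 and +0.3.

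**5. Effect of matching.** I simulated 8,000 studies (40 vs 10). One cataract candidate is considered per GA subject enrolled, in bands 60-69, 70-79 and 80 or over. A band is open while it holds fewer controls than its share of 10 among GA subjects so far.

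| | Unmatched | Matched |
|---|---|---|
| Mean age gap (years) | 7.4 | 3.1 |
| False positives, r = 0 | 5.0% | 5.1% |
| False positives, r = -0.2 | 9.0% | 5.5% |
| False positives, r = -0.3 | 14.1% | 5.9% |
| Power for -1 SD, r = +0.3 | 48% | 68% |

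Over control means of 70 to 74 and nominal gaps of 5 to 10 years, the residual gap is 2.0 to 3.9 years.

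**The case against.** The strongest objection is that confounding needs both an age gap and an age trend in aqueous alpha-MSH, and the protocol documents neither. Earlier surgery because of age does not mean that GA patients are older than people having surgery now. Some controls come from the same retina clinics. Every size above depends on assumed ages and correlations and, for error rates and power, on a test the protocol does not state. At r = -0.1 the false-positive rate barely moves. All of this stands, and it limits the point to a risk of unknown size and direction.

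A second objection is that age adjustment and reporting belong in the analysis plan, which is not shown. That is right for the form of adjustment. It does not answer the selection of controls, since no analysis can supply older controls who were never recruited. Some overlap is nevertheless likely: on the base assumptions, 76% of control sets include at least one person aged 80 or over.

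Third, the remedy is partial. In a further simulation of 4,000 studies about 13% of matched studies still had a gap above 5 years. In about 20%, more than 40 candidates were needed, so control recruitment ran on after GA enrolment ended. Matching on age also leaves the differences in lens status and sampling setting untouched. These are real limits, but the matched design still performs clearly better when a trend exists and loses nothing in error rate when there is none.

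**Conclusion.** The concern holds as a preventable design risk. The protocol rests its hypothesis on a GA-versus-control contrast, draws most of the two groups from different stages relative to cataract surgery, and sets no age rule beyond a floor of 60. Whether bias would arise is unknown. On the assumptions above it ranges from nothing to about -2.6 pM against a normal mean of 20 pM at a 7.4-year gap, with false positives between 5% and about 14%. A trend in the other direction could cut power from 79% to 47%. The change is recommended because it is cheap and must be made before controls are recruited. It is not essential to the study, and confidence is moderate.

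**What to change.** In Selection of Subjects, add: *The 10 concurrent controls will be frequency-matched by age (60-69, 70-79, 80 and over) to the GA subjects enrolled to date, and age will be reported by group.* In practice a band stays open while it holds fewer controls than its share of 10 among the GA subjects so far, so GA ages need not be known in advance. This wording also settles that the floor of 60 covers controls.

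In Background & Significance, amend the sentence on control sources so that the 8 published eyes are shown separately, as a reference, because the protocol does not give their ages. Leave the form of any age adjustment to the analysis plan.

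The cost is two sentences, a running tally by age band, and slower control recruitment. On the assumed ages about 31 cataract patients are considered for 10 places (90th percentile 49). The mean is 21 to 47 over nominal gaps of 5 to 10 years and control means of 70 to 74, and about 16 even with no gap. No extra eyes or procedures are needed. Waiting until all GA ages are known would reduce the residual gap to about 1.8 years. It would, however, collect every control sample after the GA samples, which is unattractive for a peptide the protocol describes as easily degraded.
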